8.3.3. Insulin Treatment Satisfaction Questionnaire (ITSQ)

Overall and domain will be summarized and tabulated for ITSQ score at 24 and 48 weeks for each treatment group. Table should contain the number of subjects in each treatment group, mean, SD, median, min and max. A two-sample t-test for differences between treatment arms will be performed.

8.3.4. SEITQ = Self-efficacy about Insulin Therapy Questionnaire (SEITQ)

Categorical responses for the each question will be summarized at baseline and endpoint (24 weeks). The change in SEITQ score from baseline at 24 weeks for each treatment group will be presented and P-value will be show in tables. The descriptive statistics (n, mean, median,

standard deviation, minimum, and maximum) and P-value of a two-sample t-test will be reported also.

8.3.5. The Incidences and Rates of Other Categories of Hypoglycemia

The incidences and rates of other categories of hypoglycemia (documented symptomatic, asymptomatic, unspecified, probable symptomatic and relative hypoglycemia), if available, during the 24-week and 48-week treatment period will be presented for each treatment group. Tests for differences between treatment arms will be performed. P-value of fish's exact test will be reported also.

8.4. Safety Analyses

All safety analyses specified in this subsection will be performed on the randomized population unless otherwise specified. All safety endpoints will be listed for each subject at each planned visit.

8.4.1. Adverse Event

General AEs will be collected in this study. Count and frequency of AEs will be summarized for overall study population and by treatment arm. Also, AEs as a cause for insulin treatment change will be collected, and summarized by treatment arm. Serious adverse events will be collected and reported per Lilly standard operating procedure (SOP) and local regulatory requirement. Count and frequency of SAEs will be summarized by treatment arm.

Adverse events (AEs) and treatment-emergent adverse events (TEAEs) will be coded using the MedDRA dictionary. AEs and TEAEs will be categorized by system organ class and preferred term and will be presented. TEAEs are defined as AEs occurring during or after the initial dose of study drug. AEs documented prior to initial dose cannot be classified as TEAEs unless there is a worsening in severity during or after the initial dose of study drug. The overall incidence of TEAEs with all causalities will be summarized as the number and percentage subjects in each of the categories: TEAE, TEAEs leading to insulin treatment change, SAE.

The following summaries will be presented at both the subject (number [%] of subjects) and event (number of events) level:

- AEs by SOC, PT, and treatment
- Treatment-emergent AEs by SOC, PT, and treatment
- Treatment-emergent AEs by SOC, PT, maximum severity, and treatment
- SAE by SOC, PT, and treatment
- SAE related to study drug by SOC, PT, and treatment

- Treatment-emergent AEs leading to treatment insulin treatment change by SOC, PT, and treatment
- Treatment-emergent AEs related to study drug by SOC, PT, and treatment

For the incidence at the subject level by SOC and PT, if a subject experiences more than one event within the same SOC and PT, only one occurrence will be included in the incidence.

For the incidence at the subject level by SOC, PT, and severity, if a subject experiences more than one event within the same SOC and PT, only the most severe occurrence will be included in the incidence.

For the incidence at the subject level by SOC, PT, and relationship to investigational product, if a subject experiences more than one event within the same SOC and PT, only the most related occurrence will be included in the incidence.

For the summary of number of events, if a subject experiences more than one event within the same SOC and PT, all events will be counted.

All adverse events will be listed. Additional listings will include adverse events reported as reasons for insulin treatment change.

8.4.2. Laboratory Evaluation

For the treatment period of the study, descriptive statistics by treatment group will be provided at each scheduled visit with laboratory assessment. For laboratory test with quantitative value, descriptive statistics (number, mean, median, SD, minimum, and maximum) of the observed values and changes from baseline at each scheduled visit will be reported. For laboratory test with categorical value, the number and percentage of subjects in each category will be summarized by treatment group at each scheduled visit. Shift tables (abnormal low, normal, abnormal high) of baseline against each post-baseline visit will be provided for laboratory tests.

By subject listing for laboratory tests will be presented and record with abnormal value will be flagged.

8.4.3. Vital Signs

Vital signs will be summarized similar to those described for the laboratory analyses.

By subject listing for vital sign data will be presented and record with abnormal value will be flagged.

8.4.4. Severe, Nocturnal and Total Hypoglycemic Events

The incidence rate of CRF-collected severe, nocturnal and total hypoglycemic events will be summarized by visit and for the overall study duration. Comparison between treatment arms will be performed by Fisher's exact test. The overall yearly rates (events/patient/year) of

those hypoglycemic events, calculated as, for each patient, the number of episodes times 365.25 and then divided by the patient's treatment duration, will be summarized, and analyzed by a Negative-binomial regression model with treatment as fixed effects and log of (patient's treatment duration/365.25) as an offset variable.

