10.3.4. Safety Analyses

General AEs will be collected in this study. Count and frequency of AEs will be summarized for overall study population and by treatment arm. Also, AEs as a cause for insulin treatment change will be collected, and summarized by treatment arm.

Serious adverse events will be collected and reported per Lilly standard operating procedure (SOP) and local regulatory requirement. Count and frequency of SAEs will be summarized by treatment arm.

The incidence rate of CRF-collected severe, nocturnal and total hypoglycemic events will be summarized by visit and for the overall study duration. Comparison between treatment arms will be performed by Fisher's exact test. The overall yearly rates (events/patient/year) of those hypoglycemic events, calculated as, for each patient, the number of episodes times 365.25 and then divided by the patient's treatment duration, will be summarized, and analyzed by a Negative-binomial regression model with treatment as fixed effects and log of (patient's treatment duration/365.25) as an offset variable.

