5. SAMPLE SIZE DETERMINATION

The primary objective of the study will be evaluated using the classification method as proposed by Qu and colleagues (2011). With no prior hypothesis specified, the study will be considered a success if a conclusion may be reached by the classification method. With a 1:1 randomization ratio between insulin analog mid mixture BID and basal insulin analog QD, and assuming a non-inferiority margin of 0.4%, no treatment difference between mid mixture BID and basal insulin analog QD, and a common SD of 1.5% for the change from baseline in HbA1c at Week 24, 332 evaluable patients per arm will provide greater than 99% possibility for the study to reach a conclusion for primary analyses with 2-sided alpha level of 0.05. If we assume 20% of the patients will drop out without providing an evaluable post-baseline HbA1c, 415 patients per arm need to be randomized.

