6.2. Randomized population

Randomized population includes all participants who were enrolled and who were randomized to any one of the treatment groups.

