8. GENERAL STATISTICAL CONSIDERATIONS

Additional exploratory analyses of data will be conducted, as deemed appropriate.

Given the nature of this pragmatic study, both efficacy and safety analyses will be performed on randomized patients. As sensitivity analyses, certain efficacy analyses may be repeated by censoring all efficacy data after patients changed the randomized treatment regimen.

All tests of treatment effects will be conducted at a 2-sided alpha level of 0.05, unless otherwise stated.

For continuous measures, summary statistics will include at least the number of patients with data, mean, SD, median, minimum, and maximum. For categorical measures, summary statistics will include at least the number of patients with data, frequency counts, and percentages. For comparisons based on analysis models, the differences will be reported using LS means, along with 95% CIs and p-value. Sometimes, comparison on the summary statistics may be performed and p-values be provided, and such p-values should be viewed as a descriptive measure only. Unless specified otherwise, a two-sample t-test will be used for continuous measurements and Fisher's exact test will be used for categorical measurements. Mean and median will be presented with one more decimal place than the precision of the data. Standard deviation will be presented with two more decimal places than the precision of the data. Minimum and maximum will be presented with the same precision as the original data.

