As sensitivity analyses, the endpoint analyses will be repeated by censoring all efficacy data after patients changed the randomized treatment regimen at Week 24 and Week 48, Ancova analyses for row data and LOCF data at Week 24 and Week 48 separately.

3. For percentages of patients reaching treatment goals (<7%) at Week 24 and Week 48, no missing data will be imputed. Count and percentages of patients reaching treatment goals will be summarized (when calculating percentages, the denominator will be the patients with non-missing HbA1c data at Week 24 or Week 48), and also be analyzed by a logistic regression model, with logit link function, treatment as fixed effect and baseline HbA1c as continuous covariate. Adjusted odds ratio, 95% CI and P-value will be presented. Related plot will be reported.

Plots of percentages of patients reaching treatment goals by visit for each treatment will be used to display the results of endpoints.

As sensitivity analyses, the endpoint analyses will be repeated by censoring all efficacy data after patients changed the randomized treatment regimen at Week 24 and Week 48, Ancova analyses for row data and LOCF data at Week 24 and Week 48 separately.

4. Same analyses strategy (refer to above 3) will be used for the composite endpoint of patients reaching treatment goals (<7%) and did not switch from or discontinue study treatment, and did not take rescue medication. Those patients should be without switching or discontinuing study insulin, and without using rescue therapy which will be determined by the investigator following usual standard of care between insulin analog mid mixture BID and basal insulin analog QD treatments.
5. Insulin dose at each visit will be descriptively summarized by treatment groups by total daily dose (IU and IU/kg). The descriptive statistics (n, mean, median, standard deviation, minimum, and maximum) and P-value of a two-sample t-test will be reported.
6. Time to insulin treatment change will be compared between treatment arms by a log rank test. Table and related plot will be reported. Patients who did not have any insulin treatment change up to Week 48 (or up to early discontinuation) will be considered as censored at Week 48 (or time of early discontinuation) with no event. Time to insulin treatment change: Defined as time to any of: insulin treatment

discontinuation, switch, intensification or reduction in frequency. ((date of event/censored - (date of first dose of study drug) + 1.)

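### Overall hypoglycemia incidence is compared by Fisher's exact test on all randomized patients with no allowance for unequal follow-up, so on the direct reading early leavers without an episode count as event-free

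*SAP*

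**What the plan says.** Secondary endpoint 8 (SAP 3, Protocol 4) has two halves, incidences and rates, for severe, nocturnal and total hypoglycemia over 24 and 48 weeks.

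- **Incidence.** SAP 8.4.4: "The incidence rate of CRF-collected severe, nocturnal and total hypoglycemic events will be summarized by visit and for the overall study duration". Protocol 10.3.4 has the same plan and adds: "Comparison between treatment arms will be performed by Fisher's exact test".
- **Population.** SAP 8.4: "All safety analyses specified in this subsection will be performed on the randomized population unless otherwise specified". SAP 8.4.4 specifies no other. SAP 6.2 sets no condition on dosing, visits or follow-up: "Randomized population includes all participants who were enrolled and who were randomized to any one of the treatment groups".
- **Rates.** The yearly rates go into a negative-binomial model with "log of (patient's treatment duration/365.25) as an offset variable".
- **General rule.** SAP 8: "For categorical measures, summary statistics will include at least the number of patients with data, frequency counts, and percentages".
- **Dropout.** The only figure is in SAP 5: "If we assume 20% of the patients will drop out without providing an evaluable post-baseline HbA1c, 415 patients per arm need to be randomized".

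Neither document gives a percentage denominator, a censoring rule or an early-leaver rule for hypoglycemia incidence. SAP 8.4.4 also does not name the 24-week period that the endpoint requires.

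**The concern.** Episodes are recorded through the diary and the eCRF at scheduled visits and at the early termination visit. Once a patient has left the study, later episodes are not seen. Fisher's test needs one yes or no per patient. If everyone randomized is included, a patient who left without an episode at, say, Week 6 enters as a no for 48 weeks.

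This has two consequences. Incidence is diluted in both arms. And if one arm loses more patients, that arm looks safer at the same true risk. The trial is open-label and compares one with two injections a day, so unequal loss is possible, although the documents do not predict it. The comparison is a safety result in a secondary endpoint, which readers will set beside the HbA1c result.

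**Working it through.** **The plan's own figures.** They concern HbA1c only; no hypoglycemia figure is given.
- 332 / (1 − 0.20) = 415 per arm; 2 × 415 = 830 randomized; 2 × 332 = 664 evaluable. All reproduce.
- SE = 1.5 × √(2/332) = 0.1164, so the 95% CI half-width is 0.228. A conclusion needs an estimate above −0.172 or below 0.172. These regions cover every value, which agrees with the stated chance above 99%.

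**Inputs for the illustration.** From the documents: 415 per arm, the 20% allowance, and the 24- and 48-week periods. Assumed: constant and independent hazards for dropout and first episode, the true risk p, dropout by Week 48, and any arm difference in dropout.

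**Formula.** Let d be dropout by the end of the period, G = −ln(1 − d) and H = −ln(1 − p). With all randomized patients as denominator:

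crude incidence = H/(H + G) × [1 − (1 − p)(1 − d)]

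For rare events, crude/p tends to d/G, the mean fraction of the period observed.

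**Equal dropout**
- d = 0.20: d/G = 0.20/0.2231 = 0.896. This applies to 24 weeks if 20% is lost by Week 24, and to 48 weeks if 20% is lost by Week 48.
- If 20% is lost by Week 24 and the pace continues, d = 1 − 0.80² = 0.36 by Week 48, and d/G = 0.36/0.4463 = 0.807.
- Worked case, p = 30%: 0.3567/0.5798 × 0.440 = 27.1% at d = 0.20; 0.3567/0.8030 × 0.552 = 24.5% at d = 0.36.

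| True 48-week risk | Crude, 20% lost | Ratio | Crude, 36% lost | Ratio |
|---|---|---|---|---|
| 5% | 4.5% | 0.897 | 4.0% | 0.808 |
| 20% | 18.0% | 0.900 | 16.3% | 0.813 |
| 30% | 27.1% | 0.902 | 24.5% | 0.817 |
| 40% | 36.2% | 0.905 | 32.9% | 0.822 |

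**Unequal dropout, equal true risk, rare event**
- 15% versus 25% by Week 48: 0.15/0.1625 = 0.923 and 0.25/0.2877 = 0.869. Apparent risk ratio 0.869/0.923 = 0.94.
- If those are Week 24 losses that continue, Week 48 losses are 1 − 0.85² = 28% and 1 − 0.75² = 44%: 0.2775/0.3250 = 0.854 and 0.4375/0.5754 = 0.760. Apparent risk ratio 0.89.

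**Fisher's test, simulated (415 per arm, 3,000 runs, dropout by Week 48).** Rejection rate at equal true risk:

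| True risk | 20% vs 20% | 15% vs 25% | 10% vs 30% |
|---|---|---|---|
| 20% | 3.8% | 5.4% | 10.7% |
| 30% | 3.8% | 6.6% | 14.2% |
| 40% | 4.8% | 8.0% | 18.7% |

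For true risks of 30% versus 20%, power is 89.7% without dropout and 86.1% with 20% dropout in each arm. Equal loss mainly dilutes; unequal loss distorts the comparison.

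**The case against.** The strongest reply is that a population is not a denominator. SAP 8.2 also puts efficacy on randomized patients, yet for HbA1c below 7% SAP 8.2.2 says "the denominator will be the patients with non-missing HbA1c data at Week 24 or Week 48". SAP 8 asks for the number of patients with data in every categorical summary. Hypoglycemia and diary review are scheduled at each of Visits 2 to 6 and at early termination, so attendance can separate a patient seen without an episode from one not seen.

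This stands for the by-visit tables. A reader might infer that departed patients stay in every by-visit denominator, that Fisher's test is run at each visit, and that late-visit percentages are therefore badly understated. The documents do not support that: no by-visit denominator is stated, one based on patients with data is open, and the test is not tied to visits.

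The reply is weaker for the overall figure. Showing the number with data does not say whether a patient followed for six weeks is a 48-week non-event, and Fisher's test cannot use partial follow-up.

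Other replies:
- Pairing crude incidence with exposure-adjusted rates is ordinary practice. True, but the offset does nothing for the incidence half of the endpoint.
- SAP 8 calls p-values from comparisons of summary statistics descriptive. It does not say that the Fisher test for this secondary endpoint is one of these.
- Patients who leave because of hypoglycemia have already had an episode, which the early termination visit can capture. Correct: such patients count as events, so they are no part of this case.
- The 20% is an allowance for missing HbA1c, not a retention figure. Correct: HbA1c is drawn at early termination, and the Week 24 window in SAP Appendix 1 opens on day 1, so a leaver can still be evaluable.

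**Conclusion.** The point holds for overall incidence. SAP 8.4.4 and Protocol 10.3.4 compare it by Fisher's exact test on the randomized population without adjusting for follow-up. The direct reading makes an early leaver without an episode event-free for the whole period. For by-visit percentages the denominator is merely unspecified.

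The size is conditional. Understatement is about 10% (relative) at 20% dropout by Week 48, and 18 to 19% at 36%. The apparent risk ratio at equal true rare-event risk is about 0.94 for 15% versus 25% dropout by Week 48, and about 0.89 for 28% versus 44%. All of this rests on constant, independent hazards and on assumed risks, Week 48 losses and arm differences. If the arms lose patients equally, the comparison is little affected. It is a worthwhile, inexpensive correction to a secondary safety comparison and does not touch the primary analysis.

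**What to change.** In SAP 8.4.4, with Protocol 10.3.4 aligned:

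1. For the 24-week and 48-week incidences, add the Kaplan-Meier cumulative incidence of a first episode in each category (severe, nocturnal, total), censored at the last hypoglycemia assessment. Compare arms by log-rank test, with a Cox hazard ratio and 95% CI.
2. Keep the crude proportion and Fisher's test, labeled as descriptive.
3. For by-visit percentages, use as denominator the randomized patients with a hypoglycemia assessment covering that interval, and show n.

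No new data are needed: Protocol 9.4.1 already asks for the actual time of episodes. The approach matches SAP 8.2.2, which censors time to insulin treatment change at early discontinuation. Naming both periods also supplies the 24-week analysis that 8.4.4 omits.

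The cost is one extra table per category and an assumption that censoring is unrelated to hypoglycemia risk, which should be stated with the results. If a category has very few events, the hazard ratio will be imprecise or not estimable, and the counts should then carry the description.

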Secondary Analyses: For change from baseline in venous fasting plasma glucose (FPG), finger stick blood glucose (FSBG)-based fasting blood glucose (FBG), post prandial glucose (PPG) and blood glucose (BG) excursion, the analyses model will be similar to the primary analyses model, except that the comparison will be based on the treatment contrast p-value from the ANCOVA model.

For percentages of patients reaching treatment goals (<7%) at Week 24 and Week 48, no missing data will be imputed. Count and percentages of patients reaching treatment goals will be summarized, and also be analyzed by a logistic regression model, with logit link function, treatment as fixed effect and baseline HbA1c as continuous covariate.

Insulin dose at each visit will be descriptively summarized by treatment groups by total daily dose (IU and IU/kg).

Safety: The incidence rate of case report form (CRF) collected severe, nocturnal and total hypoglycemic events will be summarized by visit and for the overall study duration. Pairwise comparison between treatment arms will be performed by Fisher's exact test. The overall yearly rates (events/patient/year) of those hypoglycemic events, calculated as, for each patient, the number of episodes times 365.25 and then divided by the patient's treatment duration, will be summarized, and analyzed by a negative-binomial regression model with treatment as fixed effects and log of (patient's treatment duration/365.25) as an offset variable.

Other Analyses: For the medial resource utilization and patient-reported outcome measurements summary statistics will be provided and comparison will be performed by appropriate general test.

Subgroup analysis will be performed for baseline HbA1c, baseline morning PPG, BG excursion, gender, and persistence levels in 2 treatment groups.

2. Schedule of Activities

Table IOQR.1. Schedule of Activities for Prospective Cohorts

eCRF Visit No.:	1	2	3	4	5	6	ET ^a
Week of treatment	0	4	12	24	36	48	ET
Visit Window (days)	–	±7	±7	±7	±14	±14	±14
Informed consent (before procedures/tests)	X						
Demographics	X						
Weight	X	X	X	X	X	X	X
Height	X						
Local urine pregnancy test ^b	X						
Duration of diabetes	X						
Anti-hyperglycemic medications(Non-insulin)	X	X	X	X	X	X	X
Insulin treatment ^c	X	X	X	X	X	X	X
Insulin dose ^d	X	X	X	X	X	X	X
Preexisting conditions/Adverse events ^e	X	X	X	X	X	X	X
Severe, nocturnal and total hypoglycemia events ^f	X	X	X	X	X	X	X

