Other categories of hypoglycemia events (if available) ^g	X	X	X	X	X	X	X
HbA1c	X ^h			X ⁱ		X ⁱ	X ⁱ
Venous FPG ^j	X			X		X	X
2-point FSBG (pre-breakfast FBG and post-breakfast PPG) ^k	X			X		X	X
Randomization	X						
SEITQ	X			X		X	X
ITSQ				X		X	X
Healthcare resource utilization	X		X	X	X	X	X
Patient training	X						
Dispense study diary and instruct to use	X	X	X	X	X		
Review study diary		X	X	X	X	X	X

Abbreviations: eCRF = electronic case report form; ET = early termination; FBG = fasting blood glucose; FPG = fasting plasma glucose; FSBG = finger stick blood glucose; HbA1c = hemoglobin A1c; ITSQ = Insulin Treatment Satisfaction Questionnaire; No. = number; PPG = post prandial glucose; SEITQ = Self-efficacy about Insulin Therapy Questionnaire.

- a Early termination (ET) visit is conducted within 14 days after the decision of discontinuation. At ET visit, fasting laboratory samples will be collected if possible.
- b A urine pregnancy test will be performed locally only for women of childbearing potential.
- c The current insulin treatment regimen, insulin treatment pattern change from last visit including insulin discontinuation, switch, intensification and reduction in frequency, and reason for insulin treatment pattern change will be recorded
- d For Visit 1, prescribed daily insulin dose by the physician will be recorded. For the following visits, actual daily insulin dose of day prior to the visit will be recorded. If the insulin treatment is temporarily suspended or discontinued before the visit, the actual daily insulin dose of the day in which the patient received his/her last insulin treatment will be recorded.
- e After the informed consent form (ICF) is signed, study site personnel will record the occurrence and nature of each patient's preexisting conditions. In addition, site personnel will record any change in the condition(s) and any new conditions as AEs.
- f Severe, nocturnal and total hypoglycemia events will be collected and analyzed as secondary endpoints.
- g Other categories of hypoglycemia (documented symptomatic, asymptomatic, unspecified, probable symptomatic and relative hypoglycemia) events will be collected if available and analyzed as exploratory objectives
- h Blood draw is not required for patients who already have measurement prior to study entry (value within 12 weeks).
- i HbA1c will be drawn locally +/- 4 weeks of visit date

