- **Relative hypoglycemia:** An event during which typical symptoms of hypoglycemia, that do not require the assistance of another person, are accompanied by BG $>$ 70 mg/dL ($>$ 3.9 mmol/L), but these levels may be quickly approaching the 70 mg/dL (3.9 mmol/L) threshold. The BG level of patients with chronically poor glycemic control can decrease so rapidly that patients may report symptoms of hypoglycemia before their BG concentration is $<$ 70 mg/dL ($<$ 3.9 mmol/L). The evaluation of this category is optional. However, if a patient reports a relative hypoglycemia event where assistance from another person was received or the patient experienced significant symptoms, the study team should clarify the circumstances to ensure the event is not a severe hypoglycemia event, and report it appropriately.
- **Total hypoglycemia:** This optional category combines all cases of hypoglycemia (documented hypoglycemia or probable symptomatic hypoglycemia, including severe hypoglycemia) excluding the events of relative hypoglycemia. Nocturnal and severe hypoglycemia are special cases of documented or probable hypoglycemia. If an event of hypoglycemia falls into multiple subcategories, that event should only be counted once in this category.

All episodes of hypoglycemia should be recorded in the “Hypoglycemic Episodes” section of the electronic case report form (eCRF). If a hypoglycemic event meets the criteria of SAE (Section 9.2.1), it should also be recorded on “Serious Adverse Events” section of the eCRF (that is, recorded as an SAE).

Severe, nocturnal and total hypoglycemia events will be collected and analyzed as secondary endpoints. Other categories of hypoglycemia (documented symptomatic, asymptomatic, unspecified, probable symptomatic and relative hypoglycemia) events will be collected if available and analyzed as exploratory objectives.

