8.2.1. Primary Analyses

The primary outcome of the study is the change from baseline in HbA1c at Week 24. The null and alternative hypotheses to be tested are as follows:

$$H_0: \hat{\mu}_{\text{arm1}} = \hat{\mu}_{\text{arm2}}$$

$$H_a: \hat{\mu}_{\text{arm1}} \neq \hat{\mu}_{\text{arm2}}$$

where μ is the mean change from baseline at Week 24 for HbA1c (primary endpoint).

In this study, HbA1c will be only measured once post-baseline at Week 24, so missing measurements will not be imputed. In addition to common summary statistics for the change from baseline data, the comparison between 2 treatment arms will be conducted using an analysis of covariate (ANCOVA) model, with change from baseline in HbA1c as response, treatment as fixed effect and baseline HbA1c as a covariate. The 95% CI of LS means difference (insulin analog mid mixture BID – basal insulin analog QD) will be used to make conclusions for the comparison. Specifically, let L and U be the lower and upper limit of this CI. Then,

- If $L > -0.4\%$, the Non-inferiority (NI) of basal insulin analog QD to insulin analog mid mixture BID is established;
- If $L > 0\%$, the superiority of basal insulin analog QD to insulin analog mid mixture BID is established;
- If $U < 0.4\%$, the NI of insulin analog mid mixture BID to basal insulin analog QD is established;
- If $U < 0\%$, the superiority of insulin analog mid mixture BID to basal insulin analog QD is established;

The summary statistics for the change from baseline data includes the number of subjects in each treatment group, mean, SD, median, min and max.

The primary analyses will at least contain n, raw mean, raw SD, adjusted mean. The least-square means (LSmeans) of change from baseline for each treatment group and difference in LSmeans between treatment groups will be presented along with the associated SE and 95% CI.

As a sensitivity analyses, the primary analyses will be repeated by censoring all efficacy data after patients changed the randomized treatment regimen. These analyses will also utilize an ANCOVA model with treatment as factors and the baseline as a covariate. Related plots will also be reported. The primary efficacy endpoints will be listed for each subject at each planned visit.

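### The negative-binomial model for hypoglycemia rates has treatment as its only explanatory term; pre-specifying baseline HbA1c could tighten the rate ratio, by an amount the documents do not let one fix

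*SAP*

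**What the plan says.** SAP 8.4.4 gives one model for severe, nocturnal and total hypoglycemia rates. They are "analyzed by a Negative-binomial regression model with treatment as fixed effects", and the log of treatment duration in years is the offset. Protocol 10.3.4 has the same model: "Negative-binomial regression model with treatment as fixed effects". Protocol 9.4.1 sets the role of these outcomes: "Severe, nocturnal and total hypoglycemia events will be collected and analyzed as secondary endpoints".

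Baseline HbA1c is a covariate in the other main models. The primary ANCOVA in SAP 8.2.1 has "treatment as fixed effect and baseline HbA1c as a covariate". In SAP 8.2.2 the HbA1c MMRM also includes it, and the logistic model for reaching HbA1c below 7% has "treatment as fixed effect and baseline HbA1c as continuous covariate". No reason is given for leaving it out of the rate model.

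Both candidate covariates come from Visit 1. HbA1c is required for eligibility (protocol 6.1, criterion 4), and the Schedule of Activities allows a recent value in place of a new sample. The row "Anti-hyperglycemic medications(Non-insulin" in the same table is also marked at Visit 1. Criterion 3 requires every patient to be taking OAMs. SAP 8.1.3 groups these drugs by ATC level 1 and preferred term. Protocol 7.2 names no stratification factor.

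**The concern.** Between-patient variation that a baseline variable could explain stays in the error of the rate comparison and can widen its interval. With no stratification described, a chance imbalance in baseline HbA1c or OAM class would pass uncorrected into the rate ratio. The sample size was set on HbA1c alone (SAP 5), so precision for hypoglycemia was never planned. With a log link and no interaction, the rate ratio estimates the same quantity with or without baseline covariates, so any precision gained does not change the question.

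**Working it through.** **The plan's own figures.** None concerns hypoglycemia. The primary figures reproduce: SE = 1.5 × √(2/332) = 0.116, and the 95% half-width is 1.96 × 0.116 = 0.228. This is below 0.4, so at least one non-inferiority conclusion is practically certain (stated: above 99%). Dropout: 332/0.80 = 415 per arm, 830 in total.

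**Inputs.** From the documents: 415 per arm, 48 weeks (48 × 7/365.25 = 0.92 year), 20% dropout. Assumed, because the documents give nothing: event rate, dispersion, a rate ratio of 1.3 (log 0.262), and the strength of the covariates.

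**Approximation.** Var(log RR) ≈ (2/n) × (1/(rate × t) + k). If covariates account for variance s² of the log rate, the dispersion left after adjustment is (1 + k)/exp(s²) − 1.

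- 1 event/year, k = 1, no covariates: (2/415) × (1.087 + 1) = 0.01006, SE 0.1003.
- Same, s² = 0.1: dispersion 2/1.105 − 1 = 0.810; (2/415) × (1.087 + 0.810) = 0.00914, SE 0.0956, a 4.7% fall.
- 0.05 events/year, k from 1 to 4, s² up to 0.4: the fall is at most 3.3%.

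The formula gives every patient the same mean in the adjusted model, so it overstates the gain. It passes 10% only when the covariates are assumed to explain a lot (for example 11.3% at 2 events/year, k = 2, s² = 0.2). Nothing in the documents supports a value that high, so the simulations carry the estimate.

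**Simulation A** (250 trials per setting, 415 per arm, 2 events/year, dispersion 2, 20% leaving early). Covariate effects on the log rate are per SD of HbA1c and for an OAM class.

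| Covariate effect | SE, treatment only | SE, adjusted | Fall |
|---|---|---|---|
| −0.2 / 0.3 | 0.1173 | 0.1161 | 1% |
| −0.3 / 0.5 | 0.1197 | 0.1165 | 3% |
| −0.4 / 0.7 | 0.1241 | 0.1180 | 5% |

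Squaring the SE ratios gives about 2%, 6% and 11% more information. In the strongest row, an interval around a rate ratio of 1 goes from exp(±1.96 × 0.1241) = 0.78 to 1.28 to exp(±1.96 × 0.1180) = 0.79 to 1.26.

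**Simulation B** (400 trials per setting, 830 patients, 20% dropout, true rate ratio 1.3). Effects on the log rate are −0.15 per 1% HbA1c and +0.4 for OAM class (moderate), or −0.3 and +0.7 (strong).

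| Setting | Fall in empirical SD of log RR | Power, treatment only → adjusted |
|---|---|---|
| Not prognostic | 0% (0.121 vs 0.121) | – |
| Moderate, 1/year | 1.5% | – |
| Moderate, 2/year | 3.8% | – |
| Strong, 1/year | 6.1% | 0.557 → 0.590 |
| Strong, 2/year | 7.6% | 0.795 → 0.845 |
| Strong, 4/year | 9.6% | 0.835 → 0.900 |
| Moderate, 0.3/year | −0.8% (no gain) | 0.321 → 0.326 |
| Moderate, 0.02/year | 0.6% | 0.063 → 0.063 |

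At 1 to 4 events/year the mean log rate ratio was 0.260 to 0.271 without covariates and 0.258 to 0.268 with them (true 0.262), so adjustment left the estimand alone. At 0.02 events/year the trial expects at most 830 × 0.92 × 0.02 ≈ 15 events, and only 56% of fits were usable with either model.

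**The case against.** The strongest reply is that nothing is wrong. The treatment-only model is valid, is pre-specified, and reads the same in both documents. That stands: a reader might infer bias or an invalid comparison, and the documents do not support either.

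Three more objections stand in part.

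- **Prognostic value.** No passage says that starting HbA1c or OAM class predicts hypoglycemia. A reader might infer that adjustment is sure to tighten the rate ratio. That depends on an effect the documents do not give, and the gain may be zero.
- **Consistency.** The HbA1c models adjust for the outcome's own baseline, which hypoglycemia does not have. Insulin dose (t-test) and time to treatment change (log-rank) are also unadjusted. The omission is therefore a missed opportunity, not a contradiction.
- **The OAM covariate.** Yes/no OAM use is constant under criterion 3, and ATC level 1 does not separate OAM classes. An insulin-secretagogue indicator can vary, but it needs a derivation from preferred terms.

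One objection does not carry. SAP 8.5 plans subgroups by baseline HbA1c (below 8.4%, and 8.4% or above), and baseline values are tabulated by arm. These would show an imbalance, but neither adjusts the overall rate ratio. The planned subgroups do show why the no-interaction condition must be stated.

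**Conclusion.** This is an optional efficiency gain of low severity. The rate model adjusts for nothing, although a covariate used in the other main models is already collected and should be nearly complete. Under assumed rates of 1 to 4 events per patient-year and moderate to strong assumed effects, the standard error falls by about 1% to 10%; it falls by 0% if the covariates are not prognostic.

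Total hypoglycemia is the likeliest to benefit. Nocturnal events are a subset and may gain little: there was no gain at 0.3/year with moderate effects. A reader might extend the gain to severe events, but the calculations show essentially none for rare events. The unchanged meaning of the rate ratio rests on there being no treatment-by-covariate interaction.

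**What to change.** In SAP 8.4.4:

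1. Add continuous baseline HbA1c to the negative-binomial model for total and nocturnal rates.
2. Optionally add an indicator of insulin-secretagogue use before randomisation. Derive it from the preferred terms of drugs recorded at Visit 1, with the list of terms fixed in advance, and do not let later OAM changes alter it.
3. State in advance that severe events keep the treatment-only model. A rule to drop covariates when events turn out to be few would depend on the data.
4. Report the unadjusted rates, and the treatment-only model as a sensitivity analysis for total and nocturnal events.
5. Fix the covariates before any Visit 4 interim analysis. The study is open-label and SAP 8.6 includes key secondary objectives in that analysis, so a later choice could look data-driven.

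The cost is SAP wording, plus one derivation rule if the secretagogue indicator is used. No new data are needed. Protocol 10.3.1 allows changes that do not touch a principal feature to be described in the SAP, so this should not need an amendment; protocol 10.3.4 can be aligned at the next revision.
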